9.4.3 ANALYSIS OF THE SECONDARY OUTCOME MEASURE(S)

Using the EEG results described in 9.4.2, mean dB change from baseline will be correlated with normalized change in HDRS* as well as the other described measures. Correlations will be assessed using Pearson's r and data will be plotted against the best fit line to visualize the results.

*HDRS normalization:

$$\frac{[\text{HDRS score at Visit \#}] - [\text{HDRS score at baseline}]}{[\text{HDRS score at baseline}]}$$

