1 PROTOCOL SUMMARY

1.1 SYNOPSIS

Title:	Lupus Brain: Transcranial Alternating Current Stimulation (tACS) to Target the Neurophysiology of Depression, Cognitive Deficits, and Pain
Study Description:	
The purpose of this clinical trial is to investigate the effects of non-invasive transcranial alternating current stimulation (tACS) on patients diagnosed with lupus. We will recruit up to 72 males and non-pregnant females diagnosed with systemic lupus erythematosus (or lupus) and a diagnosis of depression. At the initial session, consent will be obtained and eligibility will be determined. Eligible participants will undergo a structural MRI as part of the screening process, then be randomized and have 5 consecutive daily, 40 minute stimulation sessions. Participants will be randomly assigned to one of three groups: sham stimulation, individualized alpha-tACS (usually 8-12 Hz), or individualized theta-tACS (individualized alpha frequency minus 4 Hz). Participation will include 1 to 11 visits. Neurophysiological measures will be taken before and after the stimulation sessions on the first and fifth days of the intervention, as well as the 2-week follow-up and 4-week follow-up visits. Psychiatric clinical assessments will be performed at baseline (Day 1 of stimulation), Day 5 of stimulation, and at both follow-up visits using the HDRS17, the Hamilton Anxiety Rating Scale (HAM-A), the Inventory of Depression and Anxiety Symptoms (IDAS), and the Comparative Pain Scale Chart. Participants will also be asked to complete self-report surveys via REDCap at a 3-month time point measured from completion of the intervention.

Objectives:	
Primary Objective: To investigate the physiological changes in patients with systemic lupus erythematosus over the course of a 5-day, 40-minute stimulation protocol, specifically changes in alpha oscillation power from resting-state EEG recordings from baseline (Day 1) to Day 5 of stimulation.
 
Secondary Objectives: To elucidate the relationship between changes in EEG and changes in depression and pain symptoms, by comparing the changes in symptoms and the change in alpha oscillation power over the course of the intervention (baseline to day 5 of stimulation).

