3 OBJECTIVES AND OUTCOME MEASURES

OBJECTIVES	OUTCOME MEASURES	JUSTIFICATION
Primary		
To investigate the physiological changes in patients with systemic lupus erythematosus over the course of a 5-day, 40-minute stimulation protocol, specifically changes in alpha oscillation power from resting-state EEG recordings from baseline (Day 1) to Day 5 of stimulation.	Resting state EEG recordings taken on Day 1 and Day 5 of stimulation.	The protocol is for a 5-day intervention. The primary objective is focused on looking at the change in brain activity over the course of the intervention. Long-term effects (2-week follow-up and 4-week follow-up) will be assessed as exploratory outcomes.
Secondary		
To elucidate the relationship between changes in EEG and changes in pain and depression symptoms, by comparing the changes in symptoms and the change in alpha oscillation power over the course of the intervention (baseline to day 5 of stimulation). The SF-36 will be evaluated at screening and 4-week follow-up.	Correlations between clinical assessments and alpha oscillation power (as measured by resting state EEG recordings) from Day 1 and Day 5 of stimulation.	The objective is to target engagement (i.e., if the stimulation paradigm changes brain activity); the secondary objective is to determine if this engagement resulted in behavioral changes.
Exploratory		
To investigate the outlasting effects, if any, of tACS on brain activity and clinical assessments.	Resting state EEG recordings taken on 2-week and 4-week follow up visits.	The objective is to explore if any changes in brain activity persist as long-term effects. Long-term effects are detected at the 2-week and 4-week follow ups.
To investigate whether tACS increases cognitive control signals during cognitive tasks that probe sustained attention, selective attention, and working memory.	Correlations between frontal midline alpha and theta activity (as measured from EEG recordings on D1, D5, 2-week, and 4-week follow up visits) and accuracy at cognitive	We hypothesize that tACS will improve cognitive control. In particular, we hypothesize that alpha frequency tACS will improve performance the most for tasks that require attention (sustained attention and selective attention tasks),

Lupus Brain		Version 1.8
Protocol		4 March 2022

OBJECTIVES	OUTCOME MEASURES	JUSTIFICATION

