8.1.1 PHYSIOLOGICAL CHANGES

1. Resting state EEG (RSEEG) recordings will be completed at several times during the course of the study. On Day 1 and Day 5 of the intervention week, participants will complete an eyes open RSEEG immediately before and after the 40 minutes of stimulation. This measure is used to determine the immediate after-effects of tACS on brain activity, specifically on alpha oscillation power, as well as provide a before-stimulation RSEEG on these dates to compare the baseline (Day 1) to the final day of stimulation. RSEEG will also be recorded at both follow-up visits, to determine the outlasting effects of stimulation, if any. An eyes closed RSEEG will also be collected on Day 1, Day 5, and at both follow-up visits.
2. Sustained attention task will be performed with EEG recorded. The simple reaction time task requires participants to initiate a trial by pressing a button and then when prompted push a different button. In the five-choice serial reaction time task, the task is identical except that the participant is prompted to push one of five different buttons. This task measures sustained attention during the delay period of the task between task initiation and the probe appearing.
3. Selective attention task will be performed with EEG recorded. In this task, participants are instructed to orient attention to either the left or right visual field, or to both. Then, two low contrast Gabor wavelet stimuli are displayed on the screen in the left and right visual field. Each Gabor wavelet is oriented to the left or right. Finally, participants are probed as to the orientation (left or right) of the Gabor wavelet in one visual field. The attention cue to the left or right visual field is 80% predictive of which stimuli will be texted by the probe. Selective attention is the ability to improve performance with a predictive cue relative to an informative cue or an incongruent cue.

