8.1.2 PAIN EVALUATIONS

1. The Pain Catastrophizing Scale will be assessed at baseline on Day 1 of stimulation and the 3 month follow-up. This is a questionnaire to assess self-reported pain.

2. The Comparative Pain Scale Chart will be administered at baseline, Day 1 through Day 5 of stimulation, both follow-up visits, and the 3 month follow up. This is a visual scale to assess self-reported pain.

To protect our participants during COVID-19, the assessments listed above are offered to be completed using the remote REDCap survey function (PCS and PSC).

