9.1.2 SECONDARY EFFICACY HYPOTHESIS

Null hypothesis: There is no relationship between the changes in alpha frequency power and the changes in depression (using the IDAS and HDRS), pain (using the comparative pain scale and pain catastrophizing scale), and cognition (using the sustained attention task, selective attention task, working memory task, and FSCMC).

Alternate hypothesis: There is a relationship between the changes in alpha frequency power and the changes in depression (using the IDAS and HDRS), pain (using the comparative pain scale and pain catastrophizing scale), or cognition (using the sustained attention task, selective attention task, and working memory task, and FSCMC).

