10.4 PROTOCOL AMENDMENT HISTORY

Version	Date	Description of Change	Brief Rationale
1.1	5/30/19	Addition of [name] as Co-investigator	[name], a neuroradiologist, will review MRI scans and handle incidental findings as needed.
1.2	7/25/19	Clarifying sMRI timing and safety review process Updating urine pregnancy test timing per UNC IRB stipulation Updating data blinding procedures and data sharing policy per UNC SOM COI Committee FCOI management plan for [name] CANTAB to be computerized for EEG recording	Bringing protocol in compliance with UNC IRB stipulations and COI Committee management plan Editing for clarity and typos Leverages additional scientific value from the dataset
1.3	9/4/19	Updating personnel responsibilities Updating urine pregnancy test timing Updating study layout Adding cheek swab for bartonella testing Remove NAMI from recruitment Remove pressure pain threshold Adding Pain Catastrophizing Scale Replacing FSS with FSMC Replacing STAI with IDAS Removed SLAQ, PROMIS, and ESR	[name] has left the lab, his responsibilities have been given to [name]. FSMC is a more comprehensive measure for self-reporting of cognitive fog. The IDAS is a better measure to assess the change in depression and anxiety symptoms over time. These assessments were not necessary for evaluating objectives.

1.4	11/14/19	
clarifying inclusion criteria and discontinuation criteria for YRMS, a score of greater than (>) 12 is considered a manic episode and is sufficient for screen-failure or discontinuation.
 
clarifying secondary objective, the SF-36 will be evaluated at screening and 4 week follow-up, all other measures will be evaluated at baseline to Day 5 as previously approved.
	Clarifying protocol
1.5	11/25/19	Removing blood draws to test for Bartonella	We have removed Bartonella as an exploratory outcome – thus, the data is not needed
1.6	01/24/2020	Correcting HDRS17 language in study assessments and procedures to match eligibility criteria.	Providing clarification for discrepancies

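### As section 8.1.2 is written, no post-baseline EEG visit has a Pain Catastrophizing Scale, so that named secondary correlation cannot be computed over the baseline-to-Day 5 window

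*Combined protocol and SAP*

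**What the plan says.** **The analysis.** Section 9.4.3 states that "mean dB change from baseline will be correlated with normalized change in HDRS* as well as the other described measures", using Pearson's r. The other measures are those in section 9.1.2, which lists, after depression, "pain (using the comparative pain scale and pain catastrophizing scale), and cognition".

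**The window.** The secondary objective in section 3 compares symptom changes with "the change in alpha oscillation power over the course of the intervention (baseline to day 5 of stimulation"). It makes one exception, the SF-36, which is evaluated at screening and at 4 weeks. The PCS has no such exception.

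**The pain visits.** Section 8.1.2 says: "The Pain Catastrophizing Scale will be assessed at baseline on Day 1 of stimulation and the 3 month follow-up". The next item in the same section is much fuller: "The Comparative Pain Scale Chart will be administered at baseline, Day 1 through Day 5 of stimulation, both follow-up visits", and again at 3 months.

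**The EEG visits.** Section 8.1.1 places resting EEG on Day 1 and Day 5 of the stimulation week and adds: "RSEEG will also be recorded at both follow-up visits, to determine the outlasting effects of stimulation, if any". Section 4.1 describes the 3-month contact as self-report surveys through REDCap. No EEG is planned there.

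**The HDRS ratio.** Section 9.4.3 defines normalized change as visit score minus baseline score, divided by baseline score. It gives no rule for a baseline of 0. Section 5.1 sets no minimum HDRS total; its only HDRS condition concerns the suicide item.

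**The concern.** A correlation of changes needs both quantities at baseline and at the same later visit. The plan names the PCS for such a correlation, but the section that schedules the PCS gives it no visit at which the later EEG is taken.

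One of the two named pain measures is at stake. If staff work from 8.1.2, no PCS is given on Day 5, and a questionnaire about that time point cannot be completed afterwards. The analyst would then have to drop the PCS, or replace the planned window with another one, after the data are in. If the schedule of activities does call for a Day 5 PCS, staff have two conflicting instructions and compliance may vary between participants.

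**Working it through.** The plan gives no sample size, power or effect figure for the secondary correlations, so there is none to reproduce. The check compares the visit lists.

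**Step 1. Visits, from the text of section 8**

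| Visit | Resting EEG (8.1.1) | PCS (8.1.2) | Comparative Pain Scale (8.1.2) |
|---|---|---|---|
| Day 1 (baseline) | yes | yes | yes |
| Days 2 to 4 | no | no | yes |
| Day 5 | yes | no | yes |
| 2 weeks | yes | no | yes |
| 4 weeks | yes | no | yes |
| 3 months | no | yes | yes |

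**Step 2. Matched post-baseline visits**

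- EEG after baseline: Day 5, 2 weeks, 4 weeks, so 3 visits.
- PCS after baseline: 3 months only.
- Visits in common: PCS 0 of 3; Comparative Pain Scale 3 of 3.

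The only later PCS comes well after the last EEG. The schedule's visit windows centre on study days 33 (4 weeks) and 93 (3 months), and 93 − 33 = 60 days, about two months. The gap therefore also affects the exploratory analyses at the follow-up visits (9.4.8), because neither visit has a PCS under 8.1.2.

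**Step 3. Can the schedule of activities settle it?** In the table as read from the PDF, the PCS row carries eight marks, but their columns are lost. Three other rows show why the count is no guide:

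- WHODAS 2.0 also has eight marks, although 8.1.5 gives it baseline and 3 months only.
- The blinding assessment has eight, although 8.1.5 places it on Day 5.
- Resting EEG has eight, although 8.1.1 gives four visits.

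The extracted row neither confirms nor refutes a Day 5 PCS. The original table has to be consulted.

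**Step 4. Other routes to a Day 5 PCS.** Section 7.1 allows optional PCS measurement during follow-up of participants who stop the intervention. Section 9.3 excludes those participants from the per-protocol set, so this supplies no analysable pairs.

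**Step 5. The HDRS ratio (minor).** A 2-point rise gives 2/1 = +2.00 at baseline 1, 2/4 = +0.50 at baseline 4 and 2/17 = +0.12 at baseline 17. At baseline 0 the ratio has no value. The documents give no distribution of baseline scores. If a proportion p of participants scored 0, the chance of at least one zero among the 45 evaluable participants would be 1 − (1 − p)^45. That is 36% at an assumed p of 1%, 60% at 2%, 90% at 5% and 99% at 10%. The range shows only that a zero cannot be ruled out on the text of 5.1.

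**The case against.** The strongest reply is that 8.1.2 is a drafting slip. The schedule of activities is an operative instruction: its footnote 4 requires remote activities to follow it, and section 4.1 refers to it for the questionnaires. The prose of section 8 is not a complete visit list either. The fatigue scale named in 9.1.2 has no entry in 8.1.5, and the SF-36 entry there gives no visits. The version 1.4 entry in section 10.4 says that "all other measures will be evaluated at baseline to Day 5 as previously approved", which suggests that Day 5 was intended.

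Much of this stands. A reader might infer that the Day 5 PCS will certainly be missing, and the documents do not support that. They support only that 8.1.2 disagrees with 9.1.2 read together with section 3. The reply does not remove the conflict, however. For the PCS, 8.1.2 is not silent: it lists two visits, directly above a fuller list for the other pain scale, so the difference reads as deliberate. The log entry is evidence of intent and does not change the current instruction.

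A second reply is that PCS change from Day 1 to 3 months could be correlated with alpha change from Day 1 to Day 5. The arithmetic is possible, and 9.1.2 itself names no visits. It would be a different question from the one in section 3, and no section plans it.

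A third reply is that HDRS zeros may be rare or absent, since the synopsis expects a depression diagnosis. That is fair, and it is why the HDRS point is only a note.

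**Conclusion.** The conflict holds on the current text. Under 8.1.2, 0 of 3 post-baseline EEG visits has a PCS, so the PCS correlation over the section 3 window cannot be computed. This rests on two readings: that the section 3 window applies to the PCS, since only the SF-36 is excepted, and that staff follow 8.1.2. If the original schedule has a Day 5 PCS and staff follow it, the data will exist and the remaining error is the wording of 8.1.2.

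The effect is confined to one secondary measure. A reader might infer that the secondary pain objective as a whole fails or that the primary result is weakened. Neither follows: the Comparative Pain Scale is collected at every EEG visit, and the primary analysis of alpha power does not use the PCS.

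The missing rule for a zero HDRS baseline is a small gap in specification. A reader might infer bias or lost power from the ratio; neither is claimed here, because the documents give no baseline scores from which to judge it.

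The synopsis mentions a depression diagnosis that 5.1 does not list. That is a separate inconsistency to be reconciled, and this point does not depend on it.

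**What to change.** First check the PCS row in the original schedule of activities. Then make 8.1.2, 9.1.2 and the schedule agree in one of two ways:

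1. **Collect it.** Add Day 5 to the PCS visits in 8.1.2, and to the schedule if it is absent there. The cost is one short self-report form on Day 5. The PCS is already a REDCap survey (schedule footnote 4 and 8.1.2), so no new instrument is needed. If any participants have already passed Day 5 without it, their values stay missing, and the number should be reported.
2. **Remove it.** Take the PCS out of the baseline-to-Day 5 hypothesis in 9.1.2 and rely on the Comparative Pain Scale. This adds no burden, but the secondary pain question then rests on one scale. PCS change from Day 1 to 3 months can still be described.

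In 9.4.3, add one sentence, before the data are unblinded, saying how a participant with a baseline HDRS of 0 is handled. The planned ratio can stay as it is.

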9.4 STATISTICAL ANALYSES

9.4.1 GENERAL APPROACH

All testing described below assumes a significance threshold of $p = 0.05$. All hypothesis tests that are observed to not be statistically significant will be reported as being inconclusive. Continuous data will be described using means and standard deviations, while categorical data will be described using counts/percentages. All statistical estimates of population parameters will be tabulated along with their corresponding confidence intervals (CIs).

Sensitivity analyses will be used to evaluate the robustness of the main results to reasonable perturbations of the statistical models and assumptions used.

[name] will be responsible for statistical computations for data analyses. During the initial data analysis phase, [name] will be blinded to whether data and results are from sham vs active treatment in compliance with the UNC School of Medicine Conflict of Interest Committee proposed financial conflict of interest management plan.

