9.4.2 ANALYSIS OF THE PRIMARY EFFICACY OUTCOME MEASURE(S)

We will perform spectral analysis of resting state EEG from day 1 of stimulation (baseline) to day 5 of stimulation. We will use a general linear mixed-effects model (GLMM) to assess if there is statistically significant interaction between treatment (sham/placebo, theta-tACS and alpha-tACS) and session (baseline/Day 1 of stimulation, day 5 of stimulation, 2-week follow-up, 4-week follow-up). Spectral analysis will be performed with multitapered estimation of the frequency spectrum followed by integration over the classical alpha EEG band (usually 8-12 Hz). In a separate analysis, we will perform spectral analysis of resting state EEG before and after each separate stimulation session. These analyses will be completed on the per-protocol dataset.

In our previous study, which used a 5-day protocol in patients with depression (Alexander et al., 2019), we found that a correlation between the log-transformed baseline alpha power (dB) and the alpha power changes at the end of the intervention (Day 5) in all regions. We chose to use the log-transformed baseline alpha power as a covariate. We will use this same covariate in these analyses as well.

Results from this section will be described in mean decibel (dB) change and presented using spectral images for visualization.

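### The secondary alpha–symptom correlation in 9.4.3 does not carry over the baseline-alpha covariate of 9.4.2, so baseline-related variation stays in both change variables

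*Combined protocol and SAP*

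**What the plan says.** Section 9.4.3 states that "mean dB change from baseline will be correlated with normalized change in HDRS" "as well as the other described measures". A formula headed "HDRS normalization" divides the HDRS change by the baseline HDRS. No formula or scaling is given for any other measure. The method is "Correlations will be assessed using Pearson's r". No covariate, partial correlation or baseline-adjusted change is mentioned.

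Section 9.4.2 reports, from the earlier 5-day depression trial, "a correlation between the log-transformed baseline alpha power (dB) and the alpha power changes at the end of the intervention", seen in all regions. On that ground it adopts log baseline alpha as a covariate and adds: "We will use this same covariate in these analyses as well". The size and sign of the correlation are not given.

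Section 9.4.1 adds only a general undertaking: "Sensitivity analyses will be used to evaluate the robustness of the main results". It names no adjusted correlation. Section 9.3 expects at least 45 evaluable participants.

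**The concern.** The same EEG variable is adjusted for baseline in the primary analysis and, as written, not adjusted in the secondary one. A change score contains regression towards the mean from its own baseline. If participants with high baseline alpha tend to fall and those with high baseline symptoms tend to fall, both movements enter Pearson's r along with any genuine co-movement. When the two baselines are unrelated, this is noise that shrinks r. When they are related, it adds correlation that reflects where participants started.

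Dividing by baseline HDRS does not remove the problem. It does nothing about baseline alpha, and a proportional change still depends on baseline HDRS.

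The secondary objective in section 3 asks whether target engagement went with behavioural change, and these correlations are its only stated analysis. At about 45 participants there is little power to spare.

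**Working it through.** **The plan's own figure.** No sample size, power or effect size is given for the correlation. Section 9.2 covers only the active-versus-sham comparison: difference about 2, SD about 1.2, 20 per group. Its noncentrality is (2/1.2) × √(20/2) = 5.27, so power is above 99%. The plan's claim of more than 80% is true, but it does not bear on this point.

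**Detectable correlation.** By Fisher's z at N=45, two-sided 0.05 (sidedness assumed) and 80% power: r = tanh((1.960 + 0.842)/√42) = tanh(0.432) = 0.41.

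**Model (assumed).** Standardise alpha (a) and symptoms (h) at Day 1 and Day 5:
- a2 = ρ·a1 + e_a and h2 = ρ·h1 + e_h
- corr(a1, h1) = r0, and corr(e_a, e_h) = re, the link between the changes given baseline
- one homogeneous sample, with arms ignored

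Each change has variance (1−ρ)² + (1−ρ²) = 2(1−ρ). The covariance of the changes is (1−ρ)²·r0 + (1−ρ²)·re. Hence

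correlation of plain changes = re·(1+ρ)/2 + r0·(1−ρ)/2.

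The partial correlation given both baselines is re.

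**Dilution: re = 0.4, r0 = 0.** Power is Φ(atanh(r)·√42 − 1.960), ignoring the negligible opposite tail.
- ρ = 0.5: r = 0.4 × 0.75 = 0.30; 0.3095 × 6.481 = 2.006; power 52%
- ρ = 0.7: r = 0.34; power 63%
- ρ = 0.85: r = 0.37; power 71%
- Adjusted, two covariates: atanh(0.4) × √40 = 2.679; power 76%

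**Added correlation: re = 0, r0 = 0.4.** The plain-change r is 0.4 × (1−ρ)/2 = 0.10, 0.06 and 0.03. Rejection rates are 10.0%, 6.8% and 5.4%.

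**Simulation including the planned HDRS ratio.** N=45, 20,000 replicates. Assumed HDRS mean 15, SD 5, with a floor of 3 at baseline and 0 at follow-up. Entries are rejection rates for ρ = 0.5 / 0.7 / 0.85.

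| Setting | Plain changes | HDRS ratio | Partial, both baselines |
|---|---|---|---|
| re 0.4, r0 0 | 52 / 64 / 72% | 39 / 52 / 61% | 77 / 77 / 77% |
| re 0, r0 0.4 | 9.9 / 7.0 / 5.2% | 10.6 / 7.3 / 5.4% | 5.1 / 4.9 / 5.0% |
| re 0.4, r0 0.4 | 80 / 80 / 80% | 69 / 70 / 70% | 78 / 78 / 78% |
| re 0.4, r0 −0.4 | 26 / 47 / 64% | 17 / 35 / 53% | 78 / 77 / 77% |

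Smaller runs put the first cell at up to 54%. With HDRS mean 18 the ratio gives 42 / 55 / 64% in the first row and about 73% in the third.

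**Cross-check through baseline alpha alone.** Let b = corr(baseline alpha, alpha change) and c = corr(baseline alpha, symptom change).
- With c = 0 and a partial r of 0.4, the unadjusted r is 0.4·√(1−b²). For |b| = 0.3, 0.5, 0.7 this is 0.38, 0.35, 0.29, with power 74%, 65%, 48% against 77% adjusted.
- With a partial r of 0, the unadjusted r is b·c. In the model above, b = −√((1−ρ)/2) and c = r0·b. At ρ = 0.5 and r0 = 0.4, b = −0.5 and c = −0.2, so r = 0.10, as before.

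**The case against.** **The covariate may already carry over.** Section 9.4.3 opens by pointing back to the EEG results of 9.4.2, and 9.4.2 says those results are expressed as mean dB change. The EEG variable might therefore be a covariate-adjusted output. But the quantity named in 9.4.3 is dB change from baseline, and the correlation itself has no covariate. At best the text is ambiguous, which is itself a reason to specify it.

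**A correlation of changes answers the stated question.** The objectives and 9.1.2 ask about the relationship between changes. Under that reading the 0.10 in the no-link case is a real correlation of changes, and it counts as a false positive only if the target is the association given baseline. The documents do not state that target. This stands and limits the false-positive argument. It does not answer the loss of power, nor the different treatment of the same variable in 9.4.2.

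**The effect depends on assumptions.** This also stands. With both correlations at +0.4, plain changes lose no power, and the ratio loses about 8 to 9 points (4 to 5 with HDRS mean 18). Section 2.2 reports a pain–alpha relationship in an earlier trial, but the documents give no baseline alpha–HDRS correlation.

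**It is a pilot's secondary analysis.** True, and 9.4.1 already requires confidence intervals and promises sensitivity analyses. Those are unspecified, however, and none adjusts this correlation.

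**Conclusion.** The point holds as a specification gap that should be closed before analysis. Section 9.4.3 leaves out the covariate that 9.4.2 adopts, and neither the HDRS ratio nor the general sensitivity analyses supply it. If the residual link is 0.4 and baselines are unrelated, the planned HDRS correlation has about 39–61% power against about 77% adjusted. These figures rest on assumed values of ρ, re, r0 and the HDRS distribution, and are illustrations.

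Four stronger readings are tempting and not supported:
- That raw symptom change is used. HDRS change is divided by baseline, and the scaling of the other measures is simply not stated.
- That baseline alpha drives alpha change. Section 9.4.2 reports a correlation, in another population, without size or sign.
- That the link is diluted or artefactual as a matter of fact. Each outcome is conditional on correlations the documents do not give.
- That the false-positive rate is badly inflated. Taking b and c freely, |b| = 0.7 with c = 0.5 gives about 67%. In the regression-to-the-mean model |c| = |r0|·|b|, so at ρ = 0.5 even c = 0.5 would need perfectly correlated baselines. With r0 = 0.4 the excess is 0 to about 5 or 6 points, and only if the association given baseline is the target.

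**What to change.** In 9.4.3, make the main analysis the partial correlation (or equivalent regression) of alpha change with symptom change, given log baseline alpha and the baseline score of that symptom measure, with its confidence interval. Use the plain change score for HDRS in that model, since baseline HDRS is then a covariate and the ratio is not needed. State how each of the other measures is scaled. Draw the scatter plot from the adjusted residuals. The planned Pearson's r can stay as a descriptive supplement.

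If the intention was already to use covariate-adjusted EEG values, 9.4.3 should say so and define them.

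The cost is SAP wording and two degrees of freedom; all the data are already to be collected. The estimate becomes the association given baseline, which the plan should state as its target.
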